6.3.3 Visit 1- 2nd Screening

A second fasted blood draw (>10 hours) for ALT, AST, Alkaline phosphatase, and Bilirubin will be taken to confirm the first lab results at V0. If results exceed more than 50% from first lab results, and are above the normal range, then a third test (unscheduled visit) will be repeated (only for the elevated test(s)) before V2 to determine the direction of the change. If the third test shows a continued increase greater than 25% higher than the second test in ALT Alk-P or Bilirubin the subject will be disqualified. For those that qualify, all values will be recorded on the CRF.

All participants will undergo a Fibroscan (≥300db) at the first screening visit, V0 and then, after liver enzymes and all other labs, are confirmed to be within eligibility cut-offs, (V1) an assessment of liver fat percentage (min. 12%) by MRI-PDFF examination will occur. MRI scans will be sent to a Central reader to assess the eligibility for enrolment into the trial.

Fasted blood draws (>10 hours) for Fatty Acid, oxylipins and Vitamin E analyses, Lipid panel, PBMC gene expression (in a sub-set of 40 subjects), and Inflammatory markers will occur at V1. Blood analysis of PNPLA3, HSD17b and haptoglobin will also occur at Visit 1.

6.3.4 Assessment of eligibility and randomization procedure

Based on screening examinations, imaging and lab results, the investigator will assess the subject's eligibility to be entered into the clinical study. On the *Subject Screening and Enrolment Log*, the decision whether to randomize the subject into the clinical study or not is documented. For all eligible subjects, values obtained at screening (except vital signs and FFQ) will be considered 'baseline' values. The vital signs measured at randomization will be considered baseline values. The SF-36 and FFQ at randomization will be considered baseline values.

The study staff will utilize a computer-generated IWRS to randomize all eligible subjects. Subjects will be stratified by Type 2 Diabetes diagnosis (up to 50% of sample). Subject information (e.g. visit date, gender, diabetes) will be entered into the IWRS and the subject identifier (SID) and a randomization code will be generated and recorded in the subject source documents and the electronic Case Report Form (eCRF).

6.4 Intervention phase

6.4.1 Visit 2 Randomization

The following assessments are done during Randomization:

- 1. Urine Pregnancy test (females of child-bearing potential who are not post-menopausal or surgically sterilized)
- 2. Vital signs
- 3. FFQ (<200mg/d DHA and/or <60mg/d EPA to qualify) see Appendix 1
- 4. SF-36 Questionnaire (Quality of Life) see Appendix 2
- 5. Product dispensation
- 6. AEs
- 7. Concomitant Medications

6.4.2 Phone call at one month

The following assessments are done at the one-month phone call:

- 1. AUDIT Questionnaire Interview Version
- 2. Compliance (pill count check, can do by Skype or request photo of blister cards consumed)
- 3. Adverse Events (including questions related to bleeding and infections)
- 4. Con Meds
- 5. FFQ

Reminder phone calls at months 2,4 and 5 are advised to assist with retention and check on subject compliance, no diet fluctuations, ConMeds, and AEs. Only deviations, ConMeds, and AEs are to be recorded in the eCRF from such phone calls.

6.4.3 Visit 3 (3mos Visit)

The following assessments are done during the 3 mos Visit:

- 1. Physical exam
- 2. Vital signs (heart rate, blood pressure)
- 3. Anthropometrics
- 4. FFQ (see Appendix 1)
- 5. Fasted Blood draws (>10 hours) for Clinical chemistry, CBC, Fatty Acid (DHA) and Vitamin E analyses
- 6. AUDIT Questionnaire Self- Report Version
- 7. AEs
- 8. Concomitant Medications
- 9. Compliance (pill count- subjects to return all used and unused cards in the kit)

6.4.4 Visit 4 (6mos Visit)

The following assessments are done during the 6 mos Visit:

- 1. MRI-PDFF
- 2. Fasted Blood draws (>10 hours) for Clinical Chemistry (including HbA1c and insulin), Hematology, Fatty Acid, oxylipins and Vitamin E analyses, Lipid panel, gene expression (sub-set of 40 subjects), and Inflammatory markers
- 3. Vital signs (heart rate, blood pressure)
- 4. Anthropometrics
- 5. FFQ (Appendix 1)
- 6. FIB-4 score (calculated)

- 7. AUDIT Questionnaire Self- Report Version
- 8. AEs
- 9. Concomitant Medications
- 10. Compliance (pill counts- subjects to return all used and unused cards in the kit)
- 11. SF-36 Questionnaire (Appendix 2)

7 KEY MEASUREMENTS AND ASSESSMENTS

7.1 Blood samples

7.1.1 Blood sample collection

Fasted (>10 hours) plasma and serum samples will be collected from each subject at Screening V0, second Screening V1, Visit 3, and Visit 4.

7.1.2 Blood sample storage and shipment

Whole blood (between 10-25 ml, depending on the visit) will be drawn and processed at the clinical site, according to a central lab manual. Plasma and serum or whole blood will be shipped either ambient or frozen on dry ice to the central lab the day it is drawn and should be received within 24 hours at the central lab.

7.1.3 Blood sample assessment

Clinical chemistry: Glucose, HbA1c, ALT, AST, GGT, ALK-P, eGFR/creatinine clearance, creatinine, insulin, bilirubin, (**note:** for **ALT and AST** reference ranges for HH flags are to be used to determine clinical significance (CS))

Lipid panel: total cholesterol, HDL-cholesterol, LDL-cholesterol, oxidized LDL, TGs; **Hematology**: standard panel including complete blood count with automated differential including platelets, and coagulation panel INR, and Hep A (HAVIgM) test at screening, and **Inflammatory markers** (e.g. CK-18, TNF α , IL-6) will be analysed by a central lab.

Fatty acid analyses and analyses of LC-PUFA-derived oxylipins will be performed using plasma samples at the DSM Clinical Laboratory, [name]. Approximately 1.5 mL of plasma/subject/time point (V1, V3, V4) will be aliquoted and shipped frozen on dry ice in batches from the central lab to DSM.

500uL plasma for α -tocopheryl measurement (from V1, V3, V4) will be shipped frozen on dry ice in batches from the central lab to DSM Nutritional Products:

DNP R&D Analytics, NIC-RD/A Sample Registration Office, c/o Warenannahme, [name] Phone: [name] Fax: [name]

Transcriptome analysis of Gene Expression: in a subset of 40 subjects (~10 subjects/treatment arm), whole blood (~2ml) will be collected in PAXgene blood RNA tubes. Samples will be collected at Screening V1 and at Visit 4 and will be shipped frozen using dry ice along with other blood samples to the central lab the day it is drawn. Samples will be batched shipped frozen from the central lab to DSM Nutritional Products, Kaiseraugst, Switzerland for analysis.

Genotype analyses

An aliquot of whole blood (0.5ml) from each subject will be used for DNA extraction to identify those with single-nucleotide polymorphisms (SNP) i.e. PNPLA3, HSD17b and haptoglobin. Samples will be collected at Screening V1 and will be shipped frozen using dry ice along with other blood samples to the central lab the day it is drawn. Samples will be batched shipped frozen from the central lab to Indiana University for analysis.

An additional 1 ml plasma (aliquoted into [2] 0.5ml tubes) will also be collected at V1 and V4, shipped frozen on dry ice to central lab and stored for future NAFLD biomarker use.

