2.2.3 Exploratory Endpoints

- Transcriptomic analysis of the PBMC gene expression
- PNPLA3 genotype
- HSD17b
- Haptogloblin
- LC-PUFA-derived oxylipins

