9.3.4 Exploratory variables

Transcriptome analysis of gene expression will be performed in peripheral blood mononuclear cells in a subset of (n=40) subjects (~10 subjects/ treatment arm). Changes in gene expression from baseline to end of treatment (6 months) will be examined. The analyses will be conducted by DSM. Briefly, differentially expressed genes will be analysed by ANOVA. The false discovery rate (q values) will be used to correct for multiple testing. Using the global gene expression profiling results, an extensive pathway analysis (e.g. MetaCore program and/or Ingenuity Pathway Analysis) will be conducted to better understand gene regulation, mechanisms of action and activated pathways by the various treatments in this NAFLD population.

Between group differences in plasma LC-PUFA-derived oxylipins will be analysed by ANCOVA using the relevant baseline oxylipin level as a covariate.

Sub-set analyses of PNPLA3, HSD17b and haptoglobin SNPs will be conducted on the Primary endpoint to assess potential genotypic responses to treatment.

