#### 4.3 Exploratory Endpoint(s)

- The difference after 6 months of intervention between specified treatment groups (vitamin E + DHA combination vs. placebo, vitamin E vs. placebo, DHA vs. placebo) on the hepatic fat fraction [%], adjusted for baseline, stratified by the following single nucleotide polymorphisms (SNPs):
  - PNPLA3 genotype (CC versus CG + GG)
  - HSD17b genotype (GA + GG versus AA)
  - Haptoglobin genotype (\*2/\*2 versus \*1/\*2 + \*1/\*1)
- The difference after 6 months of intervention between specified treatment groups (vitamin E + DHA combination vs. placebo, vitamin E vs. placebo, DHA vs. placebo) on the hepatic fat fraction [%], adjusted for baseline, stratified by the following demographic and baseline variables:
  - Type II diabetes (yes/no)
  - Sex (male/female)
  - Baseline FIB-4 score (low risk [<1.3] versus indeterminate/high risk [≥1.3])

  - BMI (<30 kg/m^2 [underweight/healthy] versus  $\geq$ 30 kg/m^2 [overweight/obese])
  - Age (cutoff defined by the median of the baseline distribution)
  - ALT level at baseline (cutoff defined by the median of the baseline distribution)
- Transcriptome analysis will be performed using the gene expression data of peripheral blood mononuclear cells in a subset of approximately 40 subjects that complete the intervention. Changes in gene expression from baseline to end of treatment will be examined.
- The difference after 6 months of intervention between specified treatment groups (vitamin E + DHA combination vs. placebo, vitamin E vs. placebo, DHA vs. placebo) on the LC-PUFA derived oxylipins

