# 8.4 Exploratory Endpoint Analyses

The interaction between intervention groups and each of PNPLA3, HSD17b, and haptoglobin SNPs, as well as with the specified categorical demographic and baseline variables (section 4.3), on the 6-month hepatic fat fraction will be evaluated with the model specified in the primary endpoint analysis (section 8.2) where the interaction between intervention group and respective variable (i.e. SNP, categorical variable) will also be included. A separate model for each will be constructed for each exploratory interaction. Pairwise comparisons of DHA EE + vitamin E vs. PBO, vitamin E vs. PBO, and DHA EE vs. PBO will be estimated for each genotype / category along with 95% confidence intervals and presented in forest plots.

Transcriptomics (Tx) analysis of the PBMC gene expression will follow a discovery approach. The analyses will be performed internally at DSM. In brief, the gene expression workflow will be performed as defined by the Partek Software (https://www.partek.com/). The large data set will be first visually explored using different techniques like heat maps, clustering and principal component analysis (predefined by the Tx software application). This will also trigger the thresholds to be used in further processing. ANOVA pairwise group comparisons (placebo vs the different treatments) will be applied with the goal to identify genes that are significantly differently expressed. The contrast method of Fisher's least significant difference (LSD) will be used (Gene expression workflow, Partek Software) and q-Values (FDR) will be calculated to correct for multiple testing. The q-values will be set after inspection of the whole Tx data set, but will be between q = 0.05 - 0.15, if possible. The filtering will use the change fold of +1.2 fold up- and -1.2 fold down regulation versus the placebo group with the lowest p-values

2017-1088 (PUVENAFLD) SAP Version 4.0

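### The exploratory endpoint is defined as PBMC gene expression, but the only RNA specimen described is whole blood, and no isolation step or cell-composition check is planned

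*Protocol*

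**What the plan says.** **Endpoint.** Protocol 2.2.3 lists "Transcriptomic analysis of the PBMC gene expression" among the exploratory endpoints. Protocol 6.3.3 schedules the V1 draw under the same name: "PBMC gene expression (in a sub-set of 40 subjects". Protocol 9.3.4 states: "Transcriptome analysis of gene expression will be performed in peripheral blood mononuclear cells in a subset of (n=40) subjects". SAP 4.3 agrees, "using the gene expression data of peripheral blood mononuclear cells in a subset of approximately 40 subjects that complete the intervention", and SAP 6.4 and 8.4 keep the PBMC label.

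**Specimen.** Protocol 7.1.3 describes one sample for this analysis: "whole blood (~2ml) will be collected in PAXgene blood RNA tubes". It is taken at V1 and V4, shipped frozen to the central lab on the day of the draw, and later sent in frozen batches for analysis. No separation tube, isolation step or second RNA sample appears in either document. Protocol 7.1.2 and the schedule footnotes refer to a lab manual that is not among the documents.

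**Analysis.** SAP 8.4 plans pairwise ANOVA contrasts of each active arm with placebo and q-values for multiplicity. On the fold change it says: "The filtering will use the change fold of +1.2 fold up- and -1.2 fold down regulation versus the placebo group". The resulting lists go to pathway software. No cell-composition term is mentioned.

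**Data already collected.** The hematology panel in 7.1.3 is a "standard panel including complete blood count with automated differential including platelets", and the schedule places it at V0 and V4.

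**The concern.** Whole blood and PBMC are different cell populations. RNA from whole blood comes from all the blood cells, neutrophils included, whereas the endpoint is restricted to mononuclear cells. Following the plan to the letter would therefore attach a PBMC label to whole-blood results.

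This also affects interpretation. Protocol 9.3.4 aims to learn about gene regulation and mechanisms. In a mixed specimen, a change in the proportions of cell types moves the measured level of lineage-specific genes together, even if no cell changes its expression. If the mix differed between an active arm and placebo, nothing in the plan would separate that from regulation within cells. Protocol 1.3 and 1.4 present both products as anti-inflammatory, so a treatment-related difference in leukocyte mix is conceivable. In arms of this size a chance difference is possible too.

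**Working it through.** No figure in the documents is in dispute. The main check is a comparison of the text, followed by a sizing of the consequence under stated assumptions.

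**1. Text comparison.** Six sections (Protocol 2.2.3, 6.3.3, 9.3.4; SAP 4.3, 6.4, 8.4) say PBMC. One section (Protocol 7.1.3) specifies the specimen, and it says whole blood in an RNA tube. No section connects the two with an isolation step.

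**2. Composition alone, single-lineage gene.** Assume that a transcript is made only by lymphocytes and that every leukocyte contributes equally to the RNA. Its whole-blood level is then proportional to lymphocyte share. A fall from 30% to 25% (assumed) gives 0.30/0.25 = 1.20-fold down; a rise from 30% to 36% gives 0.36/0.30 = 1.20-fold up. Both equal the SAP filter.

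**3. Less specific genes.** Let f be the mononuclear share of leukocytes and r the expression in mononuclear cells relative to other leukocytes. Signal = f·r + (1 − f). The share f1 that gives 1.2-fold from a starting share f0, with no within-cell change, is f1 = [1.2(f0·r + 1 − f0) − 1]/(r − 1). Example: f0 = 0.35 and r = 10 give f1 = (1.2 × 4.15 − 1)/9 = 0.442, a rise of 9.2 points.

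| Assumed f0 | Mononuclear-only gene | r = 10 | r = 3 |
|---|---|---|---|
| 25% | 5 points | 7.2 points | 15 points |
| 35% | 7 points | 9.2 points | 17 points |
| 45% | 9 points | 11.2 points | 19 points |

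**4. The opposite error.** If a gene is expressed equally in all leukocytes and truly changes 1.2-fold in mononuclear cells only, whole blood shows 1 + 0.2f. That is 1.05, 1.07 or 1.09 for f = 25%, 35% or 45%, below the filter.

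**5. Chance differences.** SAP 6.4 samples the first 55 randomized. At 65/65/35/35 that is 55 × 65/200 = 17.9 and 55 × 35/200 = 9.6 per arm. After the planned 10% attrition it is about 16/16/9/9. With an assumed SD of 8 points for lymphocyte share, the SE of a 16-versus-9 contrast is 8 × √(1/16 + 1/9) = 3.3 points. The probability of a difference of −5 or +6 points or beyond is P(Z < −1.5) + P(Z > 1.8) = 0.067 + 0.036, about 10% per contrast. It is about 3% at an SD of 6 and 19% at an SD of 10. These are probabilities of reaching 1.2-fold for a lymphocyte-only gene, not of entering the final list.

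**The case against.** The other side has several fair points.

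- **The endpoint is exploratory.** It is one of five in Protocol 2.2.3, concerns about 40 of 200 subjects, and is described as discovery work in SAP 8.4. This stands and limits the importance of the point.
- **The lab manual might contain an isolation step.** This cannot be excluded. But 7.1.3 fixes both tube and specimen, so such a step would contradict it, and reconciliation would be needed anyway.
- **The fold filter is not the only hurdle.** SAP 8.4 also computes q-values, with a threshold intended to lie between 0.05 and 0.15. A 1.2-fold change alone does not put a gene on a list. This stands.
- **The 1.20-fold example is a best case.** For a gene only three times higher in mononuclear cells, 15 to 19 points are needed. This stands.
- **Cell mix is not peculiar to whole blood.** PBMC are themselves a mixture of lymphocytes and monocytes, so composition could matter there too, though without neutrophils. This stands; adjusting for composition is partly a separate analytic choice.

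A reader might infer that PBMC expression can under no circumstances be recovered from these samples. That rests on knowledge of the tube that neither document supplies, and on a manual that is not available. A reader might also infer that leukocyte proportions belong in the main expression model. The V4 proportions are measured after treatment and may be affected by it. Conditioning on them changes the question and can bias the randomized comparison.

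**Conclusion.** The mismatch between specimen and endpoint is certain on the documents' own text and should be corrected. A report that follows the plan would describe whole-blood results as PBMC regulation.

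The cell-mix consequence is possible but conditional. It needs a difference in leukocyte mix between an active arm and placebo, a gene that is strongly lineage-specific, and a result that passes the q-value step. Under the assumed shares, 5 to 9 points are enough for a mononuclear-only gene, and 15 to 19 points are needed at threefold enrichment. The shares, the SDs and the equal RNA contribution per cell are assumptions; the documents give none of them. They do not support the stronger inference that cell-mix shifts would dominate the gene lists or that the pathway findings would necessarily be wrong.

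No primary or secondary result is affected.

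**What to change.** 1. **Reconcile specimen and endpoint.** If 7.1.3 is correct, rename the endpoint whole-blood gene expression in Protocol 2.2.3, 6.3.3 and 9.3.4 and in SAP 4.3, 6.4 and 8.4, and do not describe the results as PBMC regulation. If mononuclear cells are in fact isolated, 7.1.3 must describe that sample and step.
2. **Keep the planned comparison in SAP 8.4, without composition adjustment, as the main analysis.**
3. **Pre-specify one sensitivity analysis in SAP 8.4**, adjusted for leukocyte composition. Use one or two proportions from the automated differential at V0 and V4, chosen so that they are not nearly collinear (the main leukocyte proportions sum to almost 100%). Report gene lists with and without adjustment.

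**Cost.** If whole blood is the intended specimen, this takes wording changes and one additional analysis, with no new sample or visit. There are three downsides. The V4 proportions are post-treatment, so the adjusted result answers a different question: the change not explained by cell mix. The V0 count can precede the V1 RNA draw by up to about three weeks (day −28 to day −5 is 23 days), so baseline adjustment is only partial. One or two degrees of freedom are spent in small arms.

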7.2 MRI-PDFF

7.2.1 Assessment of liver fat percentage by MRI-PDFF

All subjects will undergo MRI-PDFF to determine eligibility for the trial, after all the V0 and V1 screening procedures have been completed to confirm eligibility. A minimum 12% liver fat is required for trial eligibility. One standard MRI protocol will be used at all sites and one blinded central MRI reader will analyse all MRI assessments. A study-specific MRI-PDFF protocol will be developed for all participating sites. Changes in liver fat % assessed by MRI-PDFF will be measured in localized regions of interest (ROI) within each of the liver segments. MRI-PDFF will also be performed at Visit 4 (6 mos) using the same procedures.

7.3 Other key assessments

7.3.1 Liver Fibroscan

Transient elastography (Fibroscan), a rapid measure of liver tissue stiffness, will be used at Visit 0 to assess for eligibility in the trial and will be performed **prior to MRI-PDFF**. Qualifying cut off score on Fibroscan is CAP \geq 300db. If the subject meets this cut off, then the MRI-PDFF is performed at the second screening visit.

7.3.3 Anthropometrics

Height, body weight, waist and hip circumference will be measured at Visit 0, 3 and 4 at the site. Waist to hip ratio and BMI will be calculated. Sites are advised to counsel the subjects to avoid major fluctuations in diet and exercise during the study.

7.3.4 Alcohol Consumption

At Visit 0, subjects will provide their typical weekly alcohol consumption as part of medical history to confirm eligibility requirements (>21 drinks per week in men and >14 drinks per week in women is exclusionary). Additionally, the Skinner lifetime drinking history questionnaire will be administered via a structured interview and subjects will be provided the AUDIT test - Self Report Version questionnaire to complete (with cards to remind study participants of drink equivalents) in order to determine baseline alcohol consumption history/patterns.

Following randomization, the AUDIT test will be administered at 3 additional time points during the study to monitor alcohol consumption patterns. During the one-month phone call, the AUDIT test - Interview Version will be administered by study staff. At Visits 3 and 4, the AUDIT test - Self Report Version will be provided to the subject to complete in-clinic.

Data from the AUDIT questionnaire will be used to assess whether alcohol consumption modified the treatment response.

7.3.5 Urine sample collection and storage

For all females of child-bearing potential, a urine pregnancy test (dipstick) will be conducted at the site at both Screening (Visit 0) and Randomization (Visit 2) to determine eligibility in the trial. A positive pregnancy test during screening or at randomization is exclusionary for trial eligibility. Negative results will be recorded in the eCRF.

7.3.6 Questionnaires

The Medical Outcomes Study 36-Item Short-Form Health Survey (SF-36), a quality of life assessment will be administered to subjects at Visit 2 and 4. See Appendix 2.

A validated FFQ [35] to measure LC-PUFA dietary intake (namely DHA and EPA) will be administered at visits V0, V2, phone call at 1mos, V3 and V4. See Appendix 1.

8 EARLY SUBJECT WITHDRAWAL

Subjects have the right to withdraw from the study at any time for any reason, without being obliged to give reasons and without penalty or loss of benefits to which they are entitled. The investigator also has the right to withdraw subjects from the study if this is in the best interest of the subject.

Any of the following conditions leads to premature withdrawal:

- request by subject to discontinue for any reason during the study (withdrawal of consent)
- erroneously included / randomized subject
- adverse event or concurrent illness that, in the opinion of the investigator, warrants the subject's withdrawal from intervention
- intake of concomitant medications/dietary supplements prohibited by the protocol
- volunteers who do not follow the requirements of the investigator, especially those concerning safety and/or if the subject, after his enrolment is uncooperative or not willing to comply with the protocol (non-compliant)
- failure to return (lost to follow-up)
- request by the Sponsor or regulatory agencies for termination of supplementation of an individual patient or all patients under this protocol
- pregnancy, i.e. a protocol exclusion criterion

The circumstances of any discontinuation must be documented in detail in the corresponding study disposition form in the eCRF. Whenever a subject is withdrawn from the study for whatever reason, every effort will be made to perform a final assessment to include standard medical and laboratory tests (**including a final MRI, if possible**) which would have been done upon normal completion of the study, i.e. V4. The data of the withdrawn subjects will be documented in the clinical study report and may be used in statistical analyses.

Note: Subjects who withdraw prematurely from the study will not be replaced.

Protocol no.: 2017-	Version:
1088	3

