5.4 Compliance

Compliance will be determined by capsule counts and by DHA and α -tocopheryl blood levels. Subjects must take a minimum of 80% of capsules in order to be compliant. DHA and α -tocopheryl blood levels will be used to confirm accuracy of the capsule counts. A subject may be withdrawn if non-compliant. Non-compliant subjects will not be replaced and may be removed from the per-protocol analysis.

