9.3.2 Primary endpoint analysis

Decrease in hepatic fat fraction [%] relative to baseline between Vitamin E + DHA EE combination vs. placebo, measured by MRI-PDFF after 6 months of intervention. The decrease will be analysed with a linear mixed model with the hepatic fat fraction in % at 6 months as response variable. The hepatic fat fraction in % at baseline, treatment group and diabetes status will be included as fixed effects. Site will be included as random effect. This representation is formally identical to an analysis that uses the change in hepatic fat fraction in % (6 mos vs. baseline) as response variable and the hepatic fat fraction in % at baseline, treatment group and diabetes status as fixed effects and site as random effect [Laird, N. Further comparative analyses of pre-test post-test research designs. The American Statistician 1983, 37: 329-330; O'Connell, N. Methods for Analysis of Pre-Post Data in Clinical Research: A Comparison of Five Common Methods. Journal of Biometrics and Biostatistics, 2017. 8(1):1-8.]. However, this representation is chosen since it allows for easier variance-stabilizing transformations if necessary.

Statistical tests of significance will be 2-tailed at a 5% significance level. With blinded data, the residuals of the model will be analysed visually (QQ-plots, residual plots) to determine if the model assumptions (normality, variance, homogeneity) are met. If necessary, variance-stabilizing transformations will be considered.

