9.3.6 Compliance Analysis

A compliance analysis will be performed on all randomized participants who completed the study (6 mos) and ingested at least 80% of the study product using plasma DHA levels (μ g/ml) and plasma α -tocopheryl (μ mol/L) to confirm accuracy of the pill counts. ANOVA models will be employed with treatment as a factor. Frequency counts and percentages will also be presented for subjects who were at least 80% compliant by treatment group. Differences in this categorical outcome will be assessed using Fisher's Exact Test.

9.3.7 Sample size:

Le et al.[1] report that the variability (standard deviation) of the within-subject change in liver fat [%] for a period of 24 months in a similar population and with the same measurement method (MRI-PDFF) is 7%. Expecting a within-subject 3.64% absolute reduction in liver fat for the combination group vs. placebo [1, 2] and setting α =0.05 and 80% power, n=60/arm for the combination and placebo groups are needed (G*power 3.1.9.2, two-sample t-test).

To estimate the secondary endpoints (effect vs. placebo of the components (DHA EE alone and Vitamin E alone)) with a given precision (confidence interval width) of $\pm 3\%$ of liver fat, we need n=30/arm for the DHA EE only and Vitamin E only groups, leading to a necessary sample size of 180. With 10% expected attrition, the total sample size is 200 subjects.

Subjects will be stratified by Type II Diabetes diagnosis (no greater than 50% of sample). Subjects who withdraw prematurely from the study will not be replaced.

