#### 6.1 Intent-to-Treat Population

The intent-to-treat (ITT) population will include all randomized subjects and will be analyzed according to their randomized treatment assignment. In the event that randomized subjects never started treatment, a modified intent-to-treat (mITT) population will be used which is defined as the ITT that received at least one dose of study product and at least one post randomization measurement. The primary efficacy analysis will be conducted on the ITT/mITT population.

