## 8.7 Responder Analysis

A responder will be defined as a relative decrease in hepatic fat fraction (MRI-PDFF) by 30% or higher on the end of treatment MRI as compared to the baseline MRI. The proportion of responders will be estimated, along with a 95% confidence interval, for each intervention group.

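### Protocol Section 8 does not separate stopping study product from leaving the study, so Day 180 MRIs are lost avoidably and the use of early MRIs is undefined

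*Protocol*

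**What the plan says.** **Withdrawal rule.** Protocol Section 8 states: "Any of the following conditions leads to premature withdrawal". The list includes erroneous inclusion or randomisation, an adverse event or illness that warrants withdrawal from the intervention, prohibited medications or supplements, and non-compliance. Two items are worded in terms of product only: the adverse-event item and the one on a sponsor or regulator ending supplementation. The text after the list nevertheless treats every case as withdrawal from the study.

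**Final assessment.** For withdrawn subjects Section 8 asks for the tests "which would have been done upon normal completion of the study, i.e. V4", with a final MRI if feasible. It gives no date for that MRI. Their data "may be used in statistical analyses".

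**Non-compliance.** Protocol Section 5.4 says: "A subject may be withdrawn if non-compliant". The only analytic consequence it names is possible removal from the per-protocol analysis.

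**Analysis sets.** The SAP 6.1 ITT set "will include all randomized subjects and will be analyzed according to their randomized treatment assignment". Protocol 9.3.8 also requires at least one dose. Both documents exclude eligibility failures and significant non-compliance from the per-protocol set only (Protocol 9.3.8, SAP 6.2).

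**Primary outcome.** MRI-PDFF is scheduled at V1 and at V4 (Day 180, -7 to +3). SAP 8.2 models the 6-month value. SAP 8.7 defines response "on the end of treatment MRI as compared to the baseline MRI". SAP 8.8 uses observed data only; its likelihood-based handling of missing values applies to endpoints with at least two post-randomisation time points.

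**The concern.** An ITT comparison needs the outcome at the planned time from as many randomised subjects as possible, including those who stopped product or broke a rule. Section 8 ends follow-up for several groups who may be perfectly willing to come back for one scan. Some of the triggers, such as poor compliance or starting a liver or weight-loss drug, could plausibly depend on arm or on response.

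These triggers overlap the reasons for exclusion from the per-protocol set. If such subjects have no Day 180 scan, the observed-data ITT result drifts towards the per-protocol result, although the set keeps its ITT label. If they do have a scan at some earlier date, nothing says whether it enters the model as a 6-month value. In that case the estimated effect would mix follow-up times.

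**Working it through.** **1. One subject traced through the rules.** Take a subject who starts a prohibited supplement in month 2.
- Section 8: withdrawn from the study.
- SAP 6.2: a candidate for exclusion from the per-protocol set.
- SAP 6.1: still in ITT. If some randomised subjects never started treatment, the SAP uses a modified set that also needs one dose and one post-randomisation measurement.
- SAP 8.2 and 8.8: with no later MRI there is no response value. PDFF has one post-baseline time point, so the likelihood provision in SAP 8.8 does not apply and the subject adds nothing to the comparison.
- If an MRI is done in month 2, SAP 8.2 does not say whether it is the 6-month value. The wording in SAP 8.7 could admit it.

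Elsewhere the protocol does recognise subjects who are off drug but still followed: the liver-injury table in Section 10.3.2 provides for interrupting and restarting study drug. Section 8 lacks that state.

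**2. The plan's own sample size.** Inputs: difference 3.64 points and SD 7 (Protocol 9.3.7, SAP 7.0); "setting α =0.05 and 80% power, n=60/arm for the combination and placebo groups are needed"; "Statistical tests of significance will be 2-tailed at a 5% significance level".
- Normal approximation: 2 x (1.960 + 0.842)^2 x 7^2 / 3.64^2 = 58.1, so 59 per arm.
- Exact two-sample t-test, the test the protocol names: 60 per arm, power 80.6%.
- Attrition: 180 / 0.90 = 200.

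The plan's figures reproduce.

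**3. Power if withdrawn subjects have no MRI** (exact t, 65 randomised per arm, same loss in both arms):

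| Loss | Analysed per arm | Power |
|---|---|---|
| 0% | 65 | 83.7% |
| 10% | 58.5 | 79.6% |
| 15% | 55.25 | 77.3% |
| 20% | 52 | 74.8% |

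**4. Power if early MRIs count as month 6** (assumptions: effect accrues linearly, SD 7, 65 per arm analysed, scans at half of follow-up):
- 10% of the combination arm: 3.64 x (1 - 0.10 x 0.5) = 3.46; power 79.8%.
- 20% of the combination arm: 3.64 x (1 - 0.20 x 0.5) = 3.28; power 75.4%.

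**5. Possible bias, all assumed scenarios.**
- (a) 10% of the combination arm is dropped and would have shown no effect at Day 180. As-randomised difference 0.90 x 3.64 = 3.28; reported 3.64. Overstatement 0.36, a ratio of 3.64 / 3.28 = 1.11.
- (b) The same 10% is scanned at Day 60 with linear accrual, and would have reached the full effect at Day 180. Each contributes 3.64 x 60/180 = 1.21. Understatement 0.10 x (3.64 - 1.21) = 0.24.
- (c) Withdrawal differs by 10 percentage points between arms, and withdrawn subjects are 3 points worse than completers. Shift 0.10 x 3 = 0.30.

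**6. Scale.** SE of the difference at 60 per arm: 7 x sqrt(1/60 + 1/60) = 1.28. The shifts are 0.36/1.28 = 0.28, 0.24/1.28 = 0.19 and 0.30/1.28 = 0.23 standard errors.

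**The case against.** Several stronger readings are tempting, and the documents do not support them.

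- *Section 8 moves the final MRI to the withdrawal date.* It does not say so. It describes the content of the assessment and gives no date. A scan at withdrawal is the natural reading, but what is documented is undefined timing and use.
- *Section 8 contradicts the ITT definition.* Belonging to a set and being followed up are different things. Withdrawn subjects stay in ITT, and the request for a final MRI gives partial protection.
- *There is no visit window.* There is one: V4 is Day 180, -7 to +3, and extra time needs approval and a recorded deviation. What is missing is a rule for scans outside it. The data management plan cited in SAP 10.0 is not available here and might contain one.
- *Section 5.4 conflicts with Section 8 on every trigger.* Section 5.4 deals with non-compliance only. Even there, it sets a capsule threshold of 80%, while Section 8 speaks of subjects who are unwilling to follow the protocol. The two can be partly read together, but both use the same word for the subject and differ on whether withdrawal follows.
- *All the triggers are post-randomisation events.* Erroneous inclusion normally reflects eligibility before randomisation, although the removal takes place afterwards.

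The size of the problem is also open to challenge. The 10% attrition has no breakdown and will include withdrawn consent and loss to follow-up, which no wording can recover. The sample size already allows for that 10%. Protocol 5.5.1 lists gastrointestinal effects of vitamin E in under 2% of participants, and Protocol 11.4.1 anticipates only minimal risks, so a 10-point gap between arms has no support in the documents. An observed-data ANCOVA is also unbiased if missingness depends only on the covariates in the model. SAP 8.7 estimates responder proportions without a between-arm test, so little hangs on it.

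These points limit the claim and its weight. They do not supply a route to Day 180 for a subject who has stopped product, or a rule for an early scan.

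**Conclusion.** The point holds as a gap in conduct and data rules. Section 8 merges stopping product with leaving the study, which produces avoidable missing primary outcomes when there is only one post-baseline MRI and no imputation. The timing of a withdrawal MRI, and its use in SAP 8.2 and 8.7, are undefined. Sections 8 and 5.4 disagree on non-compliance and must be reconciled. Making use of withdrawn subjects' data optional does not fit an ITT primary analysis.

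The size cannot be established from the documents. The scenarios give about 0.2 to 0.4 points, or 0.2 to 0.3 standard errors, and the direction depends on the scenario: dropping subjects can inflate the effect, while early scans can dilute it. They assign all the attrition to avoidable withdrawals, so they are illustrations. No stated sample-size figure is wrong.

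This should be fixed because it is cheap and improves the primary comparison. It is not a critical flaw. Confidence is moderate.

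**What to change.** 1. In Protocol Section 8, separate stopping product from leaving the study, without changing any clinical decision on stopping product. Keep V3 and V4, with MRI in the existing Day 180 window, for every randomised subject who has not withdrawn consent, can be contacted and can appropriately be scanned. Record the date and reason of the last dose.
2. Reconcile Sections 8 and 5.4 on whether non-compliance leads to withdrawal or only permits it.
3. In Section 8, state that the data of withdrawn subjects will be used in the ITT analysis.
4. Label a scan taken at early withdrawal as Early Termination. In SAP 8.2 and 8.7, count only scans within a stated window around Day 180 as 6-month values, and use Early Termination scans in a sensitivity analysis.

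**Cost.** Protocol and SAP wording and minor eCRF work. The V4 MRI is already scheduled for every subject. Some retained subjects will be off product, so the observed effect may be slightly smaller. If follow-up has already ended, only the analysis rules in items 3 and 4 can still be set, before database lock; lost scans cannot be recovered.
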